### **3.2 Study Population**

#### **3.2.1 Intervention and treatment as usual patient groups**

Participants (n=40) with a diagnosis of a schizophrenia spectrum disorder, based on current medical records will be recruited from the teams of the Metro South Addiction and Mental Health service (MSAMHS). Participants (n=20) that are not interested in completing CR will form the patient TAU control group and will complete the pre and post measures only. Thus, group intervention allocation selection will be based on individuals' preference to participate in CR. If a participant initially signs up to the intervention group but due to change in circumstances is unable to complete CR, they will be offered the opportunity to become part of the TAU group. Individuals that initially choose to complete CR therapy but then fail to complete more than 5 sessions will be re-allocated to the control (treatment as usual) group.

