#### **3.2.2 Healthy control group**

In addition, matched healthy controls (n=20) will be recruited from the Metro South Addiction and Mental Health community services in the Princess Alexandra Hospital district as well as from the general population via word of mouth and the snowballing effect. This will provide a benchmark to compare the clinical groups and validate the fMRI task.

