### **3.3 Number of participants**

Forty individuals with a diagnosis of schizophrenia spectrum disorder and 20 healthy individuals without a diagnosis of schizophrenia spectrum disorder. Total N is 60 participants.

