## **8. Participant Completion**

Participants are considered to have completed the study if they complete 20 sessions (equivalent to 20 hours of the program) (intervention group only) and completion of post-intervention / end assessment measures (clinical groups). The healthy control group will only be required to complete the fMRI task.

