### **9.2 Statistical Analysis**

Participants' medication dosages will be converted to olanzapine equivalents using Leucht et al. (2016) guidelines. Outcome measures will be analysed using the SPSS Version 27 software package. A series of 3 (group: intervention, patient control; healthy control) x 2 (time: baseline, post-intervention) mixed factorial ANOVAs will be conducted to evaluate the treatment group differences for each of the outcome measures. If the normality assumption is violated, non-parametric analyses will be conducted.

Standard pre-processing of the functionally weighted images is carried out using SPM12 (<http://www.fil.ion.ucl.ac.uk/spm/software/spm8>, 2013; Friston, 2003). The pre-processing steps follows: slice timing on the functional images, to correct for differences in slice acquisition times within each volume using the middle slice as reference; realignment (estimate and reslice) on the functional images, to correct for inter-scan movement within each run (defined as >3 mm translation, >2 degrees rotation); co-registration of the functional and structural images; segmentation of the structural image, with heavy regularisation (0.1) recommended for MP2-RAGE sequence; normalization of the resliced images into a standardized, stereotaxic space (according to the Montreal Neurological Institute template); and smoothing of normalized images with a 8mm full-width-at-half-maximum isotropic Gaussian kernel.

We will adopt the General Linear Model approach for event-related designs will be conducted using SPM8 (<http://www.fil.ion.ucl.ac.uk>). For the first-level analysis task-related changes in blood-

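### The 3 (group) x 2 (time) ANOVA set for every outcome needs healthy-control data that Section 8 does not require, and its group-by-time interaction is not the CR-versus-TAU test

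*Protocol*

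**What the plan says.** Protocol Section 9.2 fixes the model: "A series of 3 (group: intervention, patient control; healthy control) x 2 (time: baseline, post-intervention) mixed factorial ANOVAs will be conducted". The stated purpose is "to evaluate the treatment group differences for each of the outcome measures". It then adds: "If the normality assumption is violated, non-parametric analyses will be conducted".

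Section 8 sets out what each group must do to complete the study. The clinical groups need "completion of post-intervention / end assessment measures (clinical groups"). For the third group it says: "The healthy control group will only be required to complete the fMRI task".

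Section 3.2.1 says that TAU patients "will complete the pre and post measures only". Section 3.2.2 explains why healthy controls are recruited: "This will provide a benchmark to compare the clinical groups and validate the fMRI task". Sections 3.2 and 3.3 give 20 CR patients, 20 TAU patients and 20 healthy controls ("Total N is 60 participants").

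The later part of Section 9.2 also announces second-level fMRI analyses, one comparing patients with controls and one on the effect of CR, but gives no model or contrast for either. Section 9.1 describes a pilot and makes no power claim.

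**The concern.** A 3 x 2 mixed ANOVA needs every group measured at both times. Section 8 does not require this of healthy controls: it asks them for one kind of measure only and attaches the post-intervention assessments to the patients. The protocol therefore commits to a specific model that its own data collection does not support for most of the outcomes in Section 4.2.

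The second problem is one of purpose. The model is meant to evaluate treatment group differences, but only two of the three groups bear on treatment. Once healthy controls are in the group factor, the group-by-time test asks whether any of three mean changes differ. That can be answered yes because healthy people gain more or less than patients from repeating a learning task, with CR playing no part.

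If the text stays as it is, the analyst must decide after seeing the data whether to drop the controls, change the model, or read an omnibus result as a CR effect.

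**Working it through.** The protocol gives no sample-size or power calculation, so there is no figure to reproduce. Two checks were made.

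**1. Can the model be estimated?** A 3 x 2 cell-means model has 6 parameters: an intercept, 2 for group, 1 for time and 2 for the interaction. The rank of the design depends on which healthy-control cells hold data.

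| Healthy-control data | Filled cells | Rank | Consequence |
|---|---|---|---|
| Both times | 6 | 6 of 6 | Model runs |
| Baseline only | 5 | 5 of 6 | Healthy-control interaction term not estimable |
| None | 4 | 4 of 6 | Healthy-control effect and its interaction not estimable |

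Under Section 8, the LSP-16, BACS, SCoRS, CAINS, CDSS, BPRS and BIS/BAS fall in the last row. The task learning measures fall in the first or second row, depending on whether controls are scanned twice or once.

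**2. What does the interaction test when all cells are filled?** With two time points, the group-by-time interaction is a one-way comparison of three mean changes.

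- From the protocol: n = 20 per group, so the degrees of freedom are 2 and 3 x 20 − 3 = 57.
- Assumed, because not stated: alpha 0.05, for which the critical F(2, 57) is 3.16.
- Assumed: mean changes of 0 (CR), 0 (TAU) and d (healthy controls), in change-score SD units.

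The noncentrality is λ = n × Σ(mean change − overall mean)² = 20 × (2/3) × d².

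| d | λ | Probability that the interaction is significant |
|---|---|---|
| 0.3 | 20 × 0.667 × 0.09 = 1.20 | 14.5% |
| 0.5 | 20 × 0.667 × 0.25 = 3.33 | 33.7% |
| 0.8 | 20 × 0.667 × 0.64 = 8.53 | 72.3% |

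CR and TAU are identical in every row, so none of these rejections reflects a treatment effect. A CR-versus-TAU contrast would reject in 5% of studies in each row.

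Power is not the main reason to change. For an assumed CR-versus-TAU difference in change of 0.45 or 0.59 SD, the 1-df contrast (t with 38 df, noncentrality d × √(20/2)) has power of 28% or 44%. The 2-df test has 22% or 35% if controls' change lies midway between the two patient groups, and 28% or 45% if controls change like TAU patients. The difference lies in what a significant result means.

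**The case against.** Much can be said for the plan.

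- **The model may run where it matters most.** Aim 1 rests on the learning task, and healthy controls do supply task data. Section 8 limits which measure they need; it does not say how often. The 3 x 2 design itself implies two occasions, and the schematic in Fig 1 is not available to check. Section 8 is also not a full list of control data, since Section 3.6.2 requires a TOPF score. A reader might infer that the model cannot be run at all. The text does not support that for the task measures.
- **Other comparisons are planned.** A reader might take the ANOVA to be the only stated outcome test. The second-level analyses in Section 9.2 separate patients versus controls from the effect of CR, so it is not. They give no contrast, however, and do not repair the ANOVAs for the other outcomes.
- **Follow-up contrasts can sit in an SAP.** This is fair. The rejection rates above are correct rejections of a false omnibus null, and they mislead only if that result is read as a CR effect. Still, Section 9.2 presents this model as the evaluation of treatment differences and names no contrast.
- **The non-parametric fallback.** A reader might infer that rank methods cannot test the interaction. With two time points, a rank test on change scores does address it, and the protocol names no particular test.
- **Hypothesis 1A.** A reader might infer that the patient deficit is diluted because the group main effect averages baseline and post-CR data. The protocol never assigns Hypothesis 1A to that main effect. The effect sizes in the Introduction concern global cognition, so they cannot size such a dilution for reward learning.

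The mismatch between Sections 8 and 9.2 stands, as does the point that the interaction is not the treatment contrast.

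**Conclusion.** The concern holds in two parts. First, for the seven clinical, cognitive and questionnaire measures, the stated model is not estimable as written. If the controls simply drop out of these analyses, what remains is a 2 x 2 model in patients, so the practical harm there is limited to an unspecified change of plan. For the task measures, whether the model can be estimated depends on a repeat control scan that the readable text neither states nor rules out.

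Second, where the model can be fitted, its 2-df interaction does not isolate CR from TAU. The rates of about 15%, 34% and 72% rest on 20 complete participants per group, an assumed alpha of 0.05, and assumed differences of 0.3, 0.5 and 0.8 SD in controls' change. The protocol gives no estimate of that difference, so they show a range and are not a forecast.

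Pilot status excuses low power but not a model that does not match the data. This should be fixed, but does not threaten the study.

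**What to change.** 1. Reconcile Sections 8 and 9.2: state which measures healthy controls complete and at which visits, including whether they are scanned once or twice. Limit any three-group model to those measures and times.
2. For Hypothesis 1B and the clinical scales, use a patients-only 2 (CR, TAU) x 2 (time) model and report its 1-df interaction with a confidence interval. Fit it as a mixed model with baseline and post-intervention scores both as responses, so that patients without a post visit are retained. A model of the post score given baseline would not achieve that, because such patients add nothing to it. Groups are formed by patient preference (Section 3.2.1), so comparing change and adjusting for baseline can give different answers; name the choice in advance.
3. For Hypothesis 1A, compare all patients (n = 40) with healthy controls (n = 20) at baseline on the fMRI-task measures.
4. If normality fails, apply a permutation or rank test to the same CR-versus-TAU contrast of change.

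The cost is wording in the protocol or SAP. These contrasts need no extra participants or scans.

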### **2. Aims/Objectives:**

To investigate reward processing in individuals with Schizophrenia before and after completing a course of CR, and to compare this group with a control group of individuals with Schizophrenia and a matched non-clinical group. In addition, to explore whether working memory and negative symptoms mediate change in reward processing after CR.

**Aim 1:** To investigate reward learning in individuals with schizophrenia before and after engaging in a course of CR consisting of at least 20 sessions.

Hypothesis 1A: Participants with schizophrenia will demonstrate deficits in learning in both the social and non-social conditions. These differences in learning will be linked to aberrant activity in the dopamine system at a neural level in the prefrontal cortex and subcortical structures such as the basal ganglia compared with healthy controls.

Hypothesis 1B: Participants that complete CR will demonstrate improved learning in both the social and non-social conditions, again reflecting improved neural activity within the prefrontal and basal ganglia regions.

**Aim 2:** To investigate whether social processing working memory is a mediator of changes in reward processing following the interventions.

Hypothesis 2A: Patients with schizophrenia will show an additional deficit in social reward learning, relative to non-social reward learning.

Hypothesis 2B: CR therapy will attenuate socially specific deficits in reward learning.

**Aim 3:** To investigate whether working memory is a mediator of changes in reward processing following the interventions

Hypothesis 3A: Working memory will mediate improved reward processing in patients following CR therapy.

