**fMRI Measures:**

Structural and functional MRI images are acquired by a 3T Siemens Magnetom TrioTim system using a 12-channel head coil. The sequences acquired and their parameters are as follows:

**T1-weighted imaging:** MP2-RAGE sequence. Time to acquire image: 5:02, Inversion 1: 700ms, Inversion 2: 2220ms, repetition time (TR): 4000 ms, echo time (TE): 2.96 ms, Voxel size: 1 mm isotropic, FoV= 230 mm, 192 slices with full brain coverage,;

**T2-weighted imaging.** Fluid Attenuated Inversion Recovery (FLAIR) sequence, time to acquire image: 2:44, Repetition Time: 9000ms, Echo Time: 81ms, Inversion Time: 2500ms, Flip Angle: 150 degrees, voxel size: 0.72 x 0.72 x 5.2mm. 30 Slices with full brain coverage.

**fMRI imaging.** Functional T2\*-weighted BOLD images are acquired using a multiband, echo-planar sequence, across the whole brain (TR: 0.628 ms, TE: 30 ms, resolution: 2.4 mm isotropic, FoV: 192 mm, flip angle: 52 degrees). 54 slices with full brain coverage. During fMRI imaging, participants will complete a computerised experimental task (see below). For each task condition, approximately 720 full brain images will be acquired, providing 1440 volumes acquired in approximately 12 minutes.

**Diffusion weighted Imaging.** A NODDI (Neurite Orientation Dispersion and Density Imaging) sequence with two shells and 90 gradient directions (B1=1000 with 30 directions, B2=2500 with 60 directions) with 6 B0 measurements will be acquired in the AP phase encoding direction, and an additional 6 B0 measurements will be acquired in the PA phase encoding direction. Total acquisition time: 7:24. Time of Repetition: 4100ms, Echo time: 75ms, voxel size: 2mm isotropic, 68 slices with full brain coverage.

**Susceptibility Weighted Imaging (SWI):** Time to acquire image: 2:56, RepetitionTime: 27ms, EchoTime: 20ms, flip angle: 15 degrees, voxel size: 0.89 x 0.89 x 2.5mm. 64 slices with full brain coverage.

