oxygen-level dependent (BOLD) signal will be estimated at each voxel, for each participant. Head motion parameters will be included as a regressor to account for participant motion during the course of the experiment. A 1/128 Hz high-pass filter will be used to remove slow signal drifts, and a canonical hemodynamic response function with no derivatives will be selected. Computational Modelling ([https://en.wikipedia.org/wiki/Computational\\_model](https://en.wikipedia.org/wiki/Computational_model)) will allow the estimation of learning parameters at each point in time, during each task condition, for each participant. We will employ a Variational Bayesian framework to compute how the value of each button was estimated based on the behavioural choices made, and feedback received. This allows us to measure how learning occurred during the experimental task and the subprocesses which must underlie this learning. This provides an accurate way to calculate each participants learning rate, and learning competency, based on the computation necessary to perform the task. These learning parameters will be the primary focus of first level fMRI modelling, allowing investigation of the neural systems which carry out each learning subprocess. Second level group analyses will examine how learning in patients differed from that observed in control participants, and how Cognitive Remediation therapy altered learning efficiency and the underlying neural activity. We will correct for multiple comparisons, voxel-level threshold will be set at  $p < 0.05$  family-wise error corrected.

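### The fMRI hypotheses name prefrontal cortex and basal ganglia, but Section 9.2 fixes only a voxel-level family-wise threshold with no mask or regional test, which on the natural whole-brain reading fits them poorly

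*Protocol*

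**What the plan says.** Protocol Section 2 states the neural part of the hypotheses by region. Hypothesis 1A expects aberrant activity in patients "in the prefrontal cortex and subcortical structures such as the basal ganglia compared with healthy controls". Hypothesis 1B expects better learning after cognitive remediation (CR), "again reflecting improved neural activity within the prefrontal and basal ganglia regions".

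The fMRI Measures text in Section 4.2 says that "Functional T2\*-weighted BOLD images are acquired using a multiband, echo-planar sequence, across the whole brain", with "resolution: 2.4 mm isotropic". Section 9.2 specifies an 8 mm smoothing kernel and a first-level model in which the blood-"oxygen-level dependent (BOLD) signal will be estimated at each voxel, for each participant". The inference rule for the group maps is one sentence: "We will correct for multiple comparisons, voxel-level threshold will be set at" p < 0.05, "family-wise error corrected".

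The protocol names no region of interest, anatomical mask, small-volume correction or regional summary, and the threshold sentence states no search volume. Planned group sizes are 20 (CR), 20 (treatment as usual) and 20 (healthy controls). Section 9.1 calls the study a pilot of a possible mechanism and of the fMRI task, and gives no power calculation.

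**The concern.** A voxel-level family-wise threshold grows stricter with the volume searched. If the search is the whole brain, the study pays for every voxel although two hypotheses concern named areas. With 20 per group that cost may leave little chance of declaring a regional difference of the size usually called large.

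Section 9.1 gives as the purpose of the study a possible mechanism of CR and the fMRI task itself, so the neural contrast is central. If the rule finds little whether or not a plausible regional effect exists, an empty map tells the reader almost nothing about 1A or 1B. If masks are intended but not written down, they could be chosen after the maps have been seen.

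**Working it through.** The protocol states no power or neural effect size, so there is no figure of its own to reproduce. The check compares tests at the same family-wise error of 0.05.

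**Inputs from the Protocol.** Group sizes 20/20/20 (Sections 3.1 and 3.2); voxel-level FWE 0.05 and an 8 mm kernel (Section 9.2); 2.4 mm voxels (Section 4.2).

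**Assumptions.** Search volume 1.2 to 1.6 L for the whole brain, 25 mL for basal ganglia, 250 mL for prefrontal cortex. Achieved smoothness (FWHM) 9 to 14 mm. Standardised differences d = 0.8 and 1.0. Voxelwise tests are one-sided; a two-sided search would need a higher threshold.

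**Threshold.** Random-field theory for a t-field: solve Σ R_D·ρ_D(t) = α for t. For a sphere of volume V and radius r, R0 = 1, R1 = 4r/FWHM, R2 = 2πr²/FWHM², R3 = V/FWHM³, and ρ_D are the Euler characteristic densities. Example: V = 1,600,000 mm³ gives r = 72.6 mm. At FWHM 10 mm, R1 = 29.0, R2 = 331 and R3 = 1,600. With df = 38 and α = 0.05, t = 5.80.

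**Power at a given voxel.** P(T > t), with T noncentral t and noncentrality d·√(n1·n2/(n1+n2)). For 20 v 20 this is d·√10, df 38. For 40 v 20 it is d·√13.33, df 58. Hypothesis 1A compares patients with controls and can use 40 v 20. For 1B, 20 v 20 is the CR against treatment-as-usual contrast, with d on the scale of change.

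**Regional mean.** Two-sided 0.025 for each of two regions (the first Holm step), with the same noncentral t.

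Ranges run from 9 to 14 mm smoothness.

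| Test | Critical t | d = 0.8 | d = 1.0 |
|---|---|---|---|
| 20 v 20, whole brain 1.6 L, α 0.05 | 5.92 to 5.43 | 0.3 to 0.7% | 1.2 to 2.9% |
| 20 v 20, whole brain 1.2 L, α 0.05 | 5.81 to 5.32 | 0.3 to 0.9% | 1.4 to 3.4% |
| 20 v 20, basal ganglia 25 mL, α 0.025 | 4.65 to 4.16 | 3 to 7% | 10 to 19% |
| 20 v 20, prefrontal 250 mL, α 0.025 | 5.50 to 5.01 | 0.6 to 1.7% | 2.5 to 6% |
| 20 v 20, regional mean, α 0.025 | 2.33 | 58% | 79% |
| 40 v 20, whole brain 1.2 to 1.6 L, α 0.05 | 5.50 to 4.99 | 1 to 3% | 5 to 12% |
| 40 v 20, regional mean, α 0.025 | 2.30 | 73% | 91% |

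For 80% power at 20 v 20, the regional mean needs d of about 1.01. A given voxel under the whole-brain search needs about 2.0 to 2.2.

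**Detection anywhere in the region.** The voxelwise rows refer to one given voxel, whereas a study succeeds if any voxel in the region passes. A simulation (200 to 300 runs; 20 v 20, d = 0.8 at each affected voxel, an 18 cm³ region, 10 mm smoothness) gave:

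| Effect | Whole-brain threshold | Small volume | Regional mean |
|---|---|---|---|
| Fills region, 0.8 of variance shared across it | 6% | 32% | 70% |
| Fills region, 0.5 shared | 20% | 61% | 83% |
| Fills region, none shared | 48% | 99% | 100% |
| Focal, about 10 mm | 1% | about 10% | 2% |

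The whole-brain threshold does worst in every row. Which regional test is best depends on the extent of the effect.

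**The case against.** The strongest objection is that Section 9.2 never says whole brain. Voxel-level FWE inside a prespecified mask would satisfy the sentence as written, and mask definitions often sit in a statistical analysis plan, which is not available here. This stands in part: the whole-brain search is the default reading of whole-brain images with no mask named, not a stated rule. But the protocol already fixes the kernel, filter, response function and threshold, so the search volume belongs beside them.

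A reader might infer that a real regional effect would almost always be missed. The documents do not support that. They give no neural effect size, and detection rises for effects that are very large or widespread. At d = 1.5 the per-voxel power under the same assumptions is about 17 to 32% (20 v 20) or 50 to 68% (40 v 20), and the simulation reached 48% for a region-filling effect with no shared variance.

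A reader might also infer that any regional test does much better. That fails in two places: voxelwise correction over the whole prefrontal cortex gains little, and a mean over a large mask dilutes a focal effect. The contrast of under 1% with 58% also sets one voxel against a regional mean at the same assumed d, so it shows direction and not an exact gain.

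Finally, this is a declared pilot that claims no power. Hypothesis 1A gives the basal ganglia only as an example of subcortical structures, and Section 9.2 also seeks the neural systems behind each learning subprocess. Strict whole-brain control is a defensible guard for that wider search. These points justify keeping the whole-brain map, but they do not make it a good test of the regional hypotheses. Nothing in the protocol says that a null map would count against the mechanism, so that misreading is a risk to guard against and not a fault in the text.

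**Conclusion.** The point holds as a mismatch between regional hypotheses and an inference rule with no regional element. It is not a wrong figure or a contradiction in the protocol.

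On the whole-brain reading and the assumed volumes and smoothness, the chance of passing at a given voxel is at most about 3% at d = 1.0 for 20 v 20, and at most about 12% for 40 v 20. A regional test at equal family-wise error is more sensitive. The gain is large for a regional mean when the effect fills the region, moderate for a small basal ganglia volume, and slight for voxelwise correction over the whole prefrontal cortex.

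Every d, volume and smoothness here is an assumption. The need to state the search volume and the regional test does not depend on them. This is a worthwhile, inexpensive improvement.

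**What to change.** In Section 9.2:

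- Define atlas-based basal ganglia and prefrontal masks, fixed before any group map is examined.
- Make the confirmatory fMRI test of 1A and 1B a test within those masks, with family-wise error controlled across both regions. One option is the mean learning-regressor estimate in each mask with Holm correction. The other is small-volume voxel-level FWE at 0.025 for the basal ganglia, with a mean or smaller prespecified sub-regions at 0.025 for the prefrontal cortex.
- Choose between these on the expected extent of the effect, and record the reason.
- State the search volume for the existing voxel-level threshold, keep the whole-brain FWE map as exploratory, and say that a null whole-brain map is not evidence against the mechanism.

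The cost is a few sentences and a short extraction step, with no new participants or scans. The price is that effects outside the masks become exploratory, and a mean over a large mask can dilute a focal effect.
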